#### 9.3.2.1. Secondary Efficacy Endpoint Analyses

If the treatment effects for both co-primary endpoints are statistically significant each at 2-sided 0.05 alpha level, the key secondary endpoint of change from Baseline at Week 24 in the EHP-30 Pain Domain scores will be tested comparing the relugolix Group A versus placebo Group C at a 2-sided 0.05 alpha level. The comparison will be performed using a mixed model repeated measures approach with treatment, randomization stratification factors, and treatment by visit interaction included as fixed effects and baseline value included as a covariate and an unstructured covariance. The dependent variable (change from Baseline) for each patient at each visit will be calculated based on the visit windows specified in the Statistical Analysis Plan. Based on this model, the difference in least squares means of change from Baseline between the two groups and corresponding 95% CI and p-value will be presented at Week 24 comparing Group A with Group C.

If this key secondary endpoint is positive, additional secondary efficacy endpoints to which Type 1 error protection will be extended will be tested comparing Group A with Group C using a closed testing procedure to control the familywise error rate at a 2-sided alpha level of 0.05. The details of the closed testing procedure will be provided in the Statistical Analysis Plan, which will be finalized prior to unblinding the trial.

For endpoints evaluating the change from Baseline to Week 24/EOT, treatment comparisons will be performed using a mixed model repeated measures approach with treatment, randomization stratification factors, and treatment by visit interaction included as fixed effects and Baseline value included as a covariate. The dependent variable (change from Baseline) for each patient at each visit will be calculated based on visit windows specified in the final Statistical Analysis Plan. In addition, descriptive statistics will be provided by treatment group and by visit.

For endpoints evaluating proportions, treatment comparisons will be performed using a stratified Cochran-Mantel-Haenszel test.

The daily average sB&B scores for each patient during a specific pain assessment period will be on a continuous scale for the secondary endpoints involving sB&B items with the categories as follows: none = 0, mild = 1, moderate = 2, severe = 3.

Dyspareunia analyses will be performed only in patients who had vaginal sexual intercourse during both the Baseline pain assessment and Randomized Treatment Periods.

The comparison of Group B versus Group C with respect to the responder rates for dysmenorrhea and NMPP as well as the change from Baseline at Week 24/EOT in the EHP-30 Pain Domain scores will be performed in a similar fashion to that for the co-primary efficacy analyses comparing Group A versus Group C described above.

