- dd. Patient will enter her response(s) into a tablet device at the site. On visits when both tablet and paper questionnaires are being performed at the site, the patient should complete the tablet questionnaires *before* the paper questionnaires.
- ee. Patient will enter her response onto a paper questionnaire at the site. Paper questionnaires should be done in the following order: PGA for dysmenorrhea, PGA for NMPP, PGA for function, and EHP Work Domain.
- ff. The first Patient Global Assessment (PGA) evaluations will be done during the Screening visit.
- gg. A Patient Global Impression of Change (PGIC) score for nonmenstrual pelvic pain (NMPP) will be completed on Day R35 (-2) within the eDiary.
- hh. Collect serious adverse event information from the time of signed informed consent through the Follow-Up visit, or the date of initiation of another investigational agent or hormonal therapy affecting the hypothalamic-pituitary-gonadal axis or surgical intervention for endometriosis, whichever occurs first. Collect nonserious adverse event information from the start of the Run-In Period (or from the time of signed informed consent if event was related to a study procedure) through the Follow-Up visit, or the date of initiation of another investigational agent or hormonal therapy affecting the hypothalamic-pituitary-gonadal axis or surgical intervention for endometriosis, whichever occurs first. For patients entering the extension study, adverse event collection for this study will end at the Week 24 visit.
- ii. Patients whose menses has not resumed as of the Follow-Up visit for whom there is no explanation for the lack of resumption (eg, medical procedure or medications) will be contacted by telephone 3 (+0.5) months after the Follow-Up visit to determine if menses has resumed and questioned about factors that may affect resumption of menses.

Myovant Sciences GmbH 30 CONFIDENTIAL

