# **Exclusion Criteria**

- 1. Has a history of chronic pelvic pain that is not caused by endometriosis (eg, vaginismus, chronic pelvic infection, symptomatic hydrosalpinx, symptomatic dermoid, symptomatic corpus lutea, persistent symptomatic ovarian cyst, suspected ovarian torsion, or pelvic floor disorders);
- 2. Has had 4 or more prior laparoscopic or open abdominal or pelvic, surgical procedures for endometriosis;
- 3. During the Run-In Period, reports NMPP is "much better" on the PGIC for NMPP;
- 4. Has a transvaginal ultrasound during the Screening or Run-In Period demonstrating pathology other than endometriosis that could be responsible for or contributing to the patient's chronic pelvic pain or a clinically significant gynecological disorder determined by the investigator to require further evaluation and/or treatment during the study;
  - Note 1: Saline or gel contrast is not routinely required. Use of such contrast is required only when the endometrium cannot be evaluated or when there are ambiguous and potentially exclusionary findings on the transvaginal ultrasound or endometrial biopsy (eg, suspected intrauterine masses, equivocal endometrial findings, etc);

- Note 2: Transvaginal ultrasounds that were repeated during the Run-In Period and met criteria are acceptable;
- 5. Has any chronic pain or frequently recurring pain condition, other than endometriosis, that is treated with opioids or requires analgesics for  $\geq 7$  days per month;
- 6. Has had a surgical procedure for treatment of endometriosis within the 3 months prior to the Screening visit;
- 7. Has a history of previous non-response of NMPP or dysmenorrhea to GnRH agonists, GnRH antagonists, or depot medroxyprogesterone acetate based on patient's report or treating physician's assessment of chart documentation. Note: A partial response to these drugs is not exclusionary;
- 8. Has unexplained vaginal bleeding outside of the patient's regular menstrual period, defined as bleeding occurring > 4 days outside the patient's usual range of menses duration:
- 9. Has a weight that exceeds the weight limit of the DXA scanner or has a condition that precludes an adequate DXA measurement at the lumbar spine and proximal femur (eg, bilateral hip replacement, spinal hardware in the lumbar spine);
- 10. Has bone mineral density z-score < -2.0 at spine, total hip, or femoral neck during the Run-In Period;
- 11. Has a gastrointestinal disorder affecting absorption or gastrointestinal motility;

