# 6.3.3. Run-In Period Days R36 to End of Run-In

- As soon as feasible after the Day R35 eDiary has been completed, ensure that the patient's eDiary data have been transmitted successfully and that there are at least 24 days of scores during the period Day R1 through R35 and the PGIC for NMPP on Day R33 to R35 has been completed.
- The sponsor will determine eligibility for the patient based on the transmitted eDiary pain scores and will inform the site of the patient's eligibility status within 7 days.
- If the patient is eligible, confirm the Baseline Day 1 visit with the patient.
- The patient should be reminded to continue to record daily eDiary scores.
- The patient should be reminded to continue Run-In period study drug until the day before the Baseline Day 1.
- Record adverse events and serious adverse events.
- Record any changes to concomitant medications.

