#### 9.1. **Randomization Methods**

Central randomization will be used and treatment allocation will be 1:1:1 to relugolix plus lowdose hormonal add-back therapy (Group A), relugolix monotherapy plus placebo followed by relugolix plus low-dose hormonal add-back therapy (Group B), and placebo (Group C) (see Table 5-3 for treatment group details). Randomization will be stratified by the following factors:

• Geographic Region: North America versus Rest of World; and

• Time since surgical diagnosis of endometriosis: < 5 years versus  $\ge 5$  years.

Statistical analyses for all efficacy endpoints will incorporate these stratification factors unless otherwise specified.

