#### 9.3.1.1. **Primary Analysis**

The primary hypotheses for each of the co-primary efficacy endpoints to be tested in this study are the following:

1. Relugolix (Group A) is superior to placebo (Group C) with respect to proportion of responders at the Week 24/EOT pain assessment period based on the dysmenorrhea NRS scores recorded in a daily electronic diary and use of rescue analgesics:

Null hypothesis  $H_{01}$ :  $\pi^R \le \pi^P$  vs Alternative hypothesis  $H_{a1}$ :  $\pi^R > \pi^P$ 

2. Relugolix (Group A) is superior to placebo (Group C) with respect to proportion of responders at the Week 24/EOT pain assessment period based on the NMPP NRS scores recorded in a daily electronic diary and use of rescue analgesics:

Null hypothesis H02:  $\pi^R < \pi^P$  vs Alternative hypothesis Ha2:  $\pi^R > \pi^P$ where  $\pi^R$  and  $\pi^P$  are the responder rates for relugolix and placebo groups, respectively.

The co-primary endpoints of dysmenorrhea and NMPP responder rates will be evaluated using the mITT Population. A logistic regression model will be used to compare relugolix Group A with placebo Group C for each endpoint. The responder status will be the dependent variable; treatment will be the main effect, and Baseline pain scores and stratification factors will be the covariates. The study will be considered positive if both co-primary endpoints are statistically significant with 2-sided p-values < 0.05.

In addition, the difference in responder rates between Group A and C for each co-primary endpoint will be estimated and displayed along with their 2-sided 95% confidence intervals.

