### 9.3.2. Secondary Efficacy Endpoints

• Change from Baseline at Week 24/EOT in the EHP-30 Pain Domain scores in the relugolix 40 mg group co-administered with low-dose hormonal add-back therapy for 24 weeks versus placebo;

The change at Week 24/EOT from Baseline in EHP-30 Pain Domain comparing Group A and Group C is a key secondary endpoint to which Type 1 error protection will be extended.

Effective: 12-MAR-2018

To assist in score interpretation, a meaningful within-patient score change threshold for the EHP-30 pain domain will be determined using a similar approach as that for the primary endpoint. A responder at Week 24/EOT based on EHP-30 pain domain scores is defined as a patient who had a reduction of the determined threshold or greater from Baseline using PGA for function as the anchor. Proportion of responders at Week 24/EOT based on EHP-30 Pain Domain scores is a secondary endpoint;

The following secondary endpoints will be assessed comparing Group A with Group C. The Statistical Analysis Plan will specify to which additional secondary endpoints Type 1 error protection will be extended.

- Change from Baseline to Week 24/EOT in the mean dysmenorrhea NRS score;
- Change from Baseline to Week 24/EOT in the mean NMPP NRS score;
- Change from Baseline to Week 24/EOT in the severity scores on the PGA for dysmenorrhea
- Proportion of patients who are better or much better on the PGIC for dysmenorrhea at Week 24/EOT:
- Change from Baseline to Week 24/EOT in the severity scores on the PGA for NMPP.
- Proportion of patients who are better or much better on the PGIC for NMPP at Week 24/EOT;
- Change from Baseline to Week 24/EOT in the mean dyspareunia NRS scores.
- Proportion of patients who are better or much better on the PGIC for dyspareunia at Week 24/EOT;
- Change from Baseline to Week 24/EOT in the mean dyspareunia functional impairment on the sB&B scale:
- Change from Baseline to Week 24/EOT in severity scores on the PGA for pain;
- Proportion of responders at Week 24/EOT based on EHP-30 Pain Domain scores;
- Change from Baseline to Week 24/EOT in function impairment on the PGA for function;
- Change from Baseline to Week 24/EOT in each of the non-pain EHP-30 domains (Control and Powerlessness, Social Support, Emotional Well-Being, and Self-Image);
- Change from Baseline to Week 24/EOT in the mean dysmenorrhea functional impairment on the sB&B scale;

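### Should the Week 24 PGIC-NMPP comparison adjust for the PGIC-NMPP answer given before randomization?

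*Protocol*

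**What the plan says.** Section 9.3.2 lists among the Group A versus Group C secondary endpoints: "Proportion of patients who are better or much better on the PGIC for NMPP at Week 24/EOT". Section 9.3.2.1 gives the method: "For endpoints evaluating proportions, treatment comparisons will be performed using a stratified Cochran-Mantel-Haenszel test". Section 9.3 takes the strata from the randomization, and Section 9.1 names them as region and time since surgical diagnosis, with the rule: "Statistical analyses for all efficacy endpoints will incorporate these stratification factors unless otherwise specified".

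A PGIC-NMPP answer is also taken before randomization. Footnote gg of the Schedule of Activities states: "A Patient Global Impression of Change (PGIC) score for nonmenstrual pelvic pain (NMPP) will be completed on Day R35 (-2) within the eDiary". Section 6.3.3 has the site verify that "the PGIC for NMPP on Day R33 to R35 has been completed". Its only stated use is exclusion criterion 3: "During the Run-In Period, reports NMPP is 'much better' on the PGIC for NMPP".

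Other analyses do adjust for a baseline measurement. In the co-primary logistic model (Section 9.3.1.1), "treatment will be the main effect, and Baseline pain scores and stratification factors will be the covariates". The change-from-baseline models in Section 9.3.2.1 have "treatment by visit interaction included as fixed effects and baseline value included as a covariate".

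**The concern.** Exclusion criterion 3 removes only women who answer *much better* during run-in. A woman who answers *better* can be randomized, although she already sits in a category that counts as success at Week 24. If she simply repeats that answer, she is a success in either arm and tells us little about the drug. The answer is recorded before randomization and its completion is checked, so it could enter the analysis at no data cost. The co-primary and change-from-baseline models already use a baseline value, so its absence here looks like an oversight.

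At stake would be power on one secondary endpoint. Bias is not in question, and the co-primary endpoints do not depend on this test.

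**Working it through.** **1. Is the planned test valid?** The R35 answer precedes randomization, so it is balanced between arms in expectation and leaving it out causes no bias. In a simulation with no treatment effect (20,000 trials per setting; 160 or 200 per arm; success 30% in other women and 30, 60 or 85% in women *better* at R35), type I error was 4.8 to 5.3% for the planned CMH test. It was 4.8 to 5.4% for a logistic model with treatment, region, years since diagnosis and R35. The Monte Carlo standard error is 0.15 points.

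**2. The plan's own power figure.** Section 9.3.1.3 claims at least 95% per co-primary endpoint with 200 per arm, 20% dropout, a placebo rate of 30 to 35% and a 20-point difference. Evaluable n = 200 × 0.8 = 160 per arm.

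Power = Φ{[d − 1.96·√(2p̄(1−p̄)/n)] / √[(p₁(1−p₁)+p₂(1−p₂))/n]}

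- 30 v 50%: (0.2 − 1.96 × 0.05477)/0.05362 = 1.73, power 95.8%.
- 35 v 55%: (0.2 − 1.96 × 0.05562)/0.05449 = 1.67, power 95.3%.

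The figure reproduces. The protocol gives no rates for PGIC-NMPP, so every rate below is an assumption.

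**3. What would adjustment gain?** Setting: 160 per arm, four equal randomization strata, 20,000 trials per setting, other women 30 v 45%. Power in % is planned CMH → logistic with R35, when 10, 20 or 30% are *better* at R35. Gains are taken before rounding.

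| Success in women *better* at R35, C v A | 10% | 20% | 30% | Gain (points) |
|---|---|---|---|---|
| 30 v 45 (R35 not prognostic) | 79.7→79.7 | 78.9→79.1 | 79.3→79.4 | 0.1 to 0.2 |
| 50 v 65 (equal effect) | 78.2→79.4 | 78.3→79.8 | 77.1→78.9 | 1.1 to 1.8 |
| 60 v 75 (equal effect) | 77.8→79.9 | 77.1→79.9 | 77.0→80.3 | 2.2 to 3.3 |
| 70 v 80 (smaller effect) | 74.7→77.5 | 71.4→75.7 | 67.9→73.3 | 2.8 to 5.4 |
| 85 v 90 (strong carry-over) | 72.4→77.0 | 64.3→72.1 | 57.8→68.2 | 4.6 to 10.4 |

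With other women at 32.5 v 52.5%, the 20-point planning effect, an equal effect in both groups gives a gain of 0.3 to 1.1 points. A run of 6,000 trials with 52.5 v 72.5% in the 20% who were *better* gave 94.6→95.0% at 160 per arm and 98.1→98.4% at 200. With 85 v 90% the gain is 2.0, 4.4 and 8.0 points.

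**4. A second route.** If R35 explains a share R² of the outcome variance, the effective n is about n/(1−R²). At R² = 0.05, 0.10 and 0.20, power moves from 95.3–95.8% to 96.1–96.6, 96.9–97.3 and 98.2–98.5% at 20 points. At 15 points it moves from 77.7–79.4% to 79.8–81.4, 81.9–83.5 and 86.2–87.5%.

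The R² that the table rows imply is g(1−g)Δ²/[p(1−p)], where g is the share *better* and Δ is the gap in success rate between the two kinds of women. In placebo:

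- 60 v 75 row, g = 0.2: 0.16 × 0.30² / (0.36 × 0.64) = 0.06.
- 85 v 90 row, g = 0.3: 0.21 × 0.55² / (0.465 × 0.535) = 0.26.

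So the large gains by either route need R35 to explain roughly a fifth or more of the Week 24 variance.

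**5. Does R35 behave like a baseline value?** The baselines used elsewhere in the plan are pre-treatment levels of the variable being analysed. A PGIC is a rating of change and has no baseline level.

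- The R35 answer rates change on single-blind placebo, and its top category has been removed.
- The Appendix 3 item refers to when treatment in the study was started. A woman may take that at Week 24 as R1 or as Day 1. If Day 1, the two answers have different starting points and the carry-over argument loses its basis.
- Run-In may extend to R70 with randomization one day later, so the R35 answer can be 71 − 35 = 36 days old. Baseline pain, by contrast, runs to the day before the first randomized dose (Section 9.3.1).

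**The case for a change.** The best case for a change is that the protocol does name the test and does not defer it, that the R35 answer is already collected and checked, and that a logistic model with it loses practically nothing when it is uninformative (0.1 to 0.2 points in its favour in the first row). One sentence fixed before unblinding would do it. The facts behind this are accurate, and a supportive adjusted analysis in the SAP would be reasonable.

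It does not make the plan wrong:

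- **The replacement is not the co-primary model.** That model contains the Baseline pain score. Swapping in R35 drops the NMPP covariate the protocol already relies on, and nothing shows R35 to be the better predictor.
- **It has a cost.** The comparison becomes a conditional odds ratio, with the risk difference reported separately. One of three parallel PGIC endpoints would be tested differently, because footnote gg provides no R35 answer for dysmenorrhea or dyspareunia.
- **Keeping CMH and adding R35 as a stratum is no safer.** In the non-prognostic setting it loses 0.4 to 0.5 points.
- **The role of the endpoint is still open.** Sections 9 and 9.3.2 leave detailed methods and the choice of further type I error-protected endpoints to the SAP, and Section 9.1 allows exceptions to its stratification rule. If PGIC-NMPP is protected, it is reached only after both co-primaries and the EHP-30 Pain Domain succeed.

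**Conclusion.** The concern does not hold. The stratified CMH test on the randomization factors is valid, conventional and consistent with Sections 9.1 and 9.3, and leaving out the R35 answer biases nothing. The likely gain from using it is about 0 to 1 point of power at a 20-point effect and 0 to 3 points at 15 points, with the effect assumed equal in women already *better* and in the others. Gains of 8 to 10 points need 20 to 30% of women already *better* at R35, success of 85 v 90% among them, and so a much smaller effect in that group; nothing in the protocol supports this. All success rates, the share *better* at R35 and its link to Week 24 are assumptions. The SAP was not available and may already add an adjusted analysis. What remains is a preference between two sound methods for one secondary endpoint.

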#### 9.3.1.3. Sample Size Justification

The following assumptions are used to determine the sample size for this study:

- 2-sided type I error rate: 0.05;
- Randomization: 1:1:1;
- Responder rate for Group C: 30-35%;
- Difference in responder rates between Group A and Group C: 20%;
- Dropout rate: 20%.

Assuming a dropout rate of 20%, approximately 200 women in relugolix Group A and 200 women in placebo Group C will provide at least 95% power at a 2-sided 0.05 significance level to detect a 20% difference in responder rates between Group A and Group C for each individual co-primary endpoint. This will provide an overall power of at least 90% for the study to detect a 20% treatment difference for both co-primary endpoints simultaneously. The responder rate for Group C is assumed to be between 30 and 35%. The proposed fixed sample size of 400 patients in Groups A and C is adequate to detect the target difference of 20% in responder rates between the two groups. It is calculated considering overall responder rates of close to 50% from which the maximum sample size is reached. With an additional 200 women in relugolix Group B, the total sample size will be approximately 600 women.

The assumed responder rate of 30 to 35% for Group C is within the range of responder rates (approximately 25 to 40%) observed in similar phase 3 endometriosis trials [Taylor, 2017]. The sample size and power calculations are based on the chi-squared test and were performed using the software package *nQuery* 4.0.0.0 (Statistical Solutions Ltd.).

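### The EHP-30 Pain Domain responder endpoint is tested without Baseline EHP-30, unlike the similarly built co-primary responders: a loss of efficiency and consistency, not a bias

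*Protocol*

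**What the plan says.** Protocol Section 9.3.2.1 sets one test for the secondary proportions: "For endpoints evaluating proportions, treatment comparisons will be performed using a stratified Cochran-Mantel-Haenszel test". Section 9.3 says that stratified analyses use the randomization factors, which are region and years since diagnosis.

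The EHP-30 Pain Domain responder endpoint is one of these proportions. Section 9.3.2 lists it for Group A versus C and for Group B versus C. Its threshold "will be determined using a similar approach as that for the primary endpoint", and a responder "is defined as a patient who had a reduction of the determined threshold or greater from Baseline using PGA for function as the anchor".

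Two closely related analyses do adjust for Baseline:
- **Co-primary responders (Section 9.3.1.1).** These use logistic regression, where "treatment will be the main effect, and Baseline pain scores and stratification factors will be the covariates".
- **Continuous EHP-30 Pain Domain change (Section 9.3.2.1).** This uses a mixed model with the Baseline value as a covariate.

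For Group B versus C, the last paragraph of Section 9.3.2.1 sends the dysmenorrhea and NMPP responder rates, and the EHP-30 change, to the co-primary approach. It does not name the EHP-30 responder endpoint.

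**The concern.** Whether a woman responds depends partly on where she starts. If her score is closer to the floor of the scale than the threshold, she cannot respond on either treatment. Baseline EHP-30 is therefore likely to be prognostic for this endpoint. Section 6.10.1.4 already collects it in all patients at Baseline Day 1.

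The protocol uses the Baseline score for the co-primary responders and for the continuous version of this same score, and drops it only for the dichotomised version. It gives no reason. The general CMH sentence fits the PGIC proportions, which have no Baseline score, but it also covers the EHP-30 responder.

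At stake is some power on the endpoint intended to help interpret the key secondary endpoint, and uniform treatment of the responder endpoints within the B versus C comparison.

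**Working it through.** **Inputs from the protocol (Section 9.3.1.3, stated for the co-primaries).** "2-sided type I error rate: 0.05"; "Randomization: 1:1:1"; placebo responder rate 30 to 35%; A minus C difference 20 points; 20% dropout; about 200 women per arm; chi-squared test. None of these is stated for the EHP-30 responder.

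**Step 1. Reproduce the protocol's power.** Evaluable per arm: 200 × (1 − 0.20) = 160. With pooled rate p̄,

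power = Φ{[d − 1.96·√(2p̄(1−p̄)/n)] / √([pA(1−pA) + pC(1−pC)]/n)}.

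- pC = 0.30, pA = 0.50: (0.2 − 1.96 × 0.0548)/0.0536 = 1.73, so power is 95.8%.
- pC = 0.35, pA = 0.55: (0.2 − 1.96 × 0.0556)/0.0545 = 1.67, so power is 95.3%.
- Both endpoints, if independent: 0.958² = 91.8% and 0.953² = 90.7%.

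These agree with the stated minimum of 95% for each endpoint and 90% overall.

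**Step 2. Assumptions for the EHP-30 responder (not in the documents).** Let ρ be the correlation between Baseline and Week 24 scores, with equal SDs. The correlation of Baseline with improvement is then

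r = √((1 − ρ)/2),

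so ρ = 0.3, 0.5, 0.7 gives r = 0.59, 0.50, 0.39. There are four equal strata, unrelated to outcome. Improvement is dichotomised to give the chosen responder rates.

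**Step 3. Compare the two analyses.** Power (%) is shown as stratified CMH → logistic regression with treatment, Baseline and strata, from 4,000 simulated trials per cell. The gain in points is in brackets and was computed before rounding.

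| n per arm | pC | Difference | r = 0.59 | r = 0.50 | r = 0.39 |
|---|---|---|---|---|---|
| 160 | 30% | 20 | 95.1→98.3 (3.2) | 96.5→98.3 (1.8) | 95.6→97.1 (1.5) |
| 160 | 35% | 20 | 94.9→98.4 (3.5) | 94.9→97.5 (2.7) | 95.4→96.8 (1.5) |
| 200 | 30% | 20 | 98.6→99.8 (1.2) | 98.2→99.5 (1.2) | 98.2→98.8 (0.5) |
| 200 | 35% | 20 | 98.3→99.6 (1.3) | 98.4→99.3 (0.9) | 98.2→98.7 (0.6) |
| 160 | 30% | 15 | 79.3→88.3 (9.0) | 79.7→85.9 (6.2) | 79.2→82.6 (3.3) |
| 160 | 35% | 15 | 77.8→87.7 (9.9) | 76.9→84.2 (7.3) | 77.5→81.3 (3.8) |
| 200 | 30% | 15 | 87.3→94.0 (6.6) | 87.3→91.9 (4.6) | 86.4→89.7 (3.3) |
| 200 | 35% | 15 | 85.2→92.4 (7.3) | 85.2→90.5 (5.3) | 86.0→89.0 (3.0) |

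A logistic model without Baseline stayed within 0.5 points of CMH in every cell, so the gain comes from the covariate and not from the change of test.

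**Step 4. Sensitivity.**
- *Weak correlation.* With r of 0 to 0.2, the gain is about 0 to 2 points.
- *Smaller differences.* At 10 and 12.5 points (200 per arm, pC 35%, r 0.4 to 0.6), the gain is 4.2 to 11.1 points.
- *A different set-up.* This assumed Baseline mean 60 and SD 18, improvement SD 25, threshold 30, and 200 per arm, with 3,000 trials per setting. At a 15-point difference, power rose from 86.3 to 89.1%, 87.5 to 90.6% and 86.8 to 92.2% for r = 0.3, 0.4 and 0.5.

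**Step 5. Validity.** With no treatment effect (160 per arm, rate 32.5%, r = 0.50), the rejection rate was 5.3% for CMH and 5.1% for the adjusted model. The simulation standard error is √(0.05 × 0.95/4,000) = 0.34 points, so both agree with 5%.

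**The case against.** The case for leaving the plan alone has real weight:
- **Validity.** CMH is valid and prespecified, and it gives one method for all the secondary proportions. A reader might infer that women who cannot respond bias the comparison. They do not: randomization balances them in expectation, they lower the rate in both arms, and the simulated type I error is nominal.
- **Size.** A reader might infer a fixed loss of several points of power. The documents do not support one. The only responder difference they state is 20 points, set for the co-primaries, and there the loss is small because power is already about 95% or more. Larger losses need a smaller true difference and a moderate to strong Baseline correlation, and the protocol gives neither figure.
- **Importance.** The key secondary endpoint is the continuous change, which is already Baseline-adjusted. Whether the responder version gets type I error protection is left to the SAP, and the protocol claims no power for it.
- **Similarity.** The co-primary responder also requires no increase in rescue analgesics, so the two definitions are alike but not identical.
- **Group B versus C.** The CMH test applies there only through the general sentence, which the section's own last paragraph overrides for the dysmenorrhea and NMPP responder rates.

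All of this stands, and it limits the importance of the point. It does not justify omitting a prognostic value that is already collected, when the protocol's own model for similar endpoints would use it. Nor is the test left to the SAP: the protocol names it.

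**Conclusion.** The point holds as a minor improvement. The EHP-30 Pain Domain responder is the only responder endpoint defined by a threshold reduction from Baseline that the protocol leaves to a test without the Baseline score. The consequence is lower efficiency and inconsistent handling, with no bias and no inflation of type I error.

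Its size rests on assumptions. With r of about 0.4 to 0.6 and 160 to 200 women per arm, it is about 0.5 to 3.5 points of power at a 20-point difference and about 3 to 10 points at 15 points. With r of 0 to 0.2 it is about 0 to 2 points. The documents do not show which case applies, and they do not support calling this endpoint underpowered.

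**What to change.** In Section 9.3.2.1:
- Analyse the EHP-30 Pain Domain responder endpoint, for A versus C and for B versus C, with the co-primary logistic model: treatment, Baseline EHP-30 Pain Domain score and stratification factors.
- Name this endpoint in the section's last paragraph, beside the dysmenorrhea and NMPP responder rates.
- Limit the general CMH sentence to the PGIC proportions, and keep CMH for the EHP-30 responder as a sensitivity analysis.

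The cost is a few words of protocol text, with no new data or visits. One drawback is that the odds ratio becomes conditional on Baseline, as it already is for the co-primaries. The difference in responder rates with its 95% CI should therefore be reported as well, as Section 9.3.1.1 already does for the co-primaries. The change should be made before unblinding.
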